4.2. Definition of Study Drugs

The study drugs were:

- DFD-03 (tazarotene) Lotion 0.1% (60 mL bottle containing 50 ml of study product, [name] Ltd.)
- Vehicle Lotion (0% tazarotene) (60 mL bottle containing 50 ml of study product, [name] Ltd.)
- Tazorac (tazarotene) 0.1% Cream (60-gram tube, Allergan, Inc.)
- Vehicle Cream (0% tazarotene) (60-gram tube, [name] Ltd.)

The study products were provided by [name] Ltd., Hyderabad, India. The study products were white to off-white lotions and white to off-white creams. The ingredients of the Vehicle Lotion and Vehicle Cream were identical to DFD-03 Lotion and Tazorac Cream, respectively, except for omission of tazarotene.

4.3. Sample Size Considerations

The sample size was not powered to obtain statistical significance, but was expected to provide an estimate on comparability of local tolerability/safety of DFD-03 versus Tazorac Cream and their respective Vehicles.

4.4. Randomization

Subjects were assigned randomly to one of the four treatment arms, DFD-03 (tazarotene) Lotion 0.1%, Tazorac (tazarotene) Cream, 0.1%, Vehicle Lotion or Vehicle Cream in a 2:2:1:1 ratio (50 subjects each to DFD-03 Lotion and Tazorac Cream, and 25 subjects each to Vehicle Lotion and Vehicle Cream). A treatment assignment schedule was created with kit numbers randomly assigned to study products. The date and time of randomization and the bottle/tube number should have been entered on the eCRF.

[name], Ltd Statistical Analysis Plan, Version 2.0

For the selected site(s) enrolling subjects in the 9-11 age group, subjects were assigned randomly to one of the two treatment arms, DFD-03 (tazarotene) Lotion 0.1%, and 0.1%, Vehicle Lotion in a 1:1 ratio (4 subjects each to DFD-03 Lotion and Vehicle Lotion). A treatment assignment schedule was created with kit numbers randomly assigned to study products, which is independent from the treatment assignment schedule created for ages 12 and older.

For the selected site(s) enrolling subjects with acne involvement on the face, chest and/or back including shoulders, subjects were assigned randomly to treatment with either DFD-03 (tazarotene) Lotion 0.1%, Tazorac (tazarotene) Cream, 0.1%, Vehicle Lotion or Vehicle Cream in a 2:2:1:1 ratio. Since these subjects were treating their face, chest and/or back and shoulders, the subject kit size contained more study medication for application. A treatment assignment schedule was created for these larger kit sizes with kit numbers randomly assigned to study products, which is independent from the treatment assignment schedules created for ages 9-11 and 12 and older.

A unique subject number was assigned to each subject. The randomization number (kit number) was designated as the subject number. The subject maintained the same subject number and treatment assignment throughout the study. Subject numbers were assigned immediately prior to dispensing study medication and were assigned starting with the lowest available number at the study site.

The Investigator designated an independent third party study medication dispenser who dispensed to qualified subjects, collected all bottles/tubes of study product and dispensed and collected diaries.

No stratification based on age or other characteristics was performed.

4.5. Clinical Assessments

Clinical assessments are summarized in Table 2.

Table 2: Study Schedule

	Visit 1	Visit 2	Visit 3	Visit 4	Visit 5
	Screen ¹	Day 1 ¹	Week 4 ²	Week 8 ³	Week 12 ³
	Day -60 to 0	Baseline	Day 28	Day 56	Day 84
Informed Consent/assent	X				
Inclusion and exclusion criteria	X	X			
Medical (including acne) history / prior and concomitant medications	X	X			
Collect Demographic Data	X				
Fitzpatrick Skin Type Assessment		X			
Physical Examination (including height and weight at Baseline Visit only)		X			X
Vital signs assessment (Blood Pressure and Pulse Rate)	X	X	X	X	X
Update concomitant medication			X	X	X
Urine pregnancy test ⁴	X	X	X	X	X
Randomization		X			
Dispense/redispense study product		X	X	X	

	Visit 1	Visit 2	Visit 3	Visit 4	Visit 5
	Screen ¹	Day 1 ¹	Week 4 ²	Week 8 ³	Week 12 ³
	Day -60 to 0	Baseline	Day 28	Day 56	Day 84
Weigh study product bottles prior to dispensing and used bottles upon return		X	X	X	X
Initiate treatment		X			
Dispense/review/collect study diary		X	X	X	X
Review subject instructions		X	X	X	
Collect empty bottles			X	X	X
Evaluate IGA on face	X	X	X	X	X
Count inflammatory and non-inflammatory lesions on face	X	X	X	X	X
Count inflammatory and non- inflammatory lesions on the chest and/or back including shoulders (if applicable) ⁵		X	X	X	X
Assess for any local cutaneous tolerance/application site reactions ⁶ on face, and if applicable, separately for the chest and/or back including shoulders ⁵		X	X	X	X
CADI Questionnaire		X	X	X	X
Evaluate compliance			X	X	X
Adverse event assessment		X	X	X	X
End of study					X

End of study

1 Visit 1 and 2 may have been combined if no washout period was required, but should not have been separated by more than 60 days.

Visit window +/- 3 days
 Visit window +/- 5 days

 ⁴ For all females regardless of reproductive potential
 5 For the selected site(s) that randomized subjects who were treating chest and/or back (including shoulders)

⁶ Dryness, non-lesional erythema, peeling, stinging, burning, itching.

5. PLANNED ANALYSES

5.1. Final Analyses

Final analysis is planned for the study after the database lock. The final analysis will follow instructions presented in this SAP.

6. GENERAL CONSIDERATIONS FOR DATA ANALYSES AND HANDLING

6.1. General Summary Table and Individual Subject Data Listing Considerations

Summary tables and listings (e.g., post text tables and individual subject data listings are prepared according to ICH Guideline E3) include a "footer" providing explanatory notes that indicate as a minimum:

- 1. SAS program name.
- 2. Programmer.
- 3. Date of data extraction.
- 4. Date of output generation.

Post text tables also include reference(s) to the subject data listing(s) that supports the summary data. The data extraction date links the output to the archived database that is locked to ensure the replication of the results.

Post text tables will be organized with respect to treatment group and a column will be included to summarize all treated subjects. The order of drug presentation will be investigational drug first followed by the vehicle control. A total column will appear as the last column. The summary tables clearly indicate the number of subjects to which the data apply and unknown or not performed are distinguished from missing data.

Summary tables for medications and medical conditions are coded according the WHO Drug Dictionary. Adverse event preferred terms and body/organ systems are coded using the MedDRA dictionary. The MedDRA dictionary can be used, as well, in the coding of signs and symptoms, medical history, physical examination abnormalities, and clinical diagnoses.

Supportive individual subject data listings, as a minimum, are sorted and presented by treatment group and subject id. Listings also include visit number, visit date, and days relative to the initiation of double-blind treatment.

6.2. General Post Text Summary Table and Individual Subject Data Listing Format Considerations

The default convention is to number tables and listings using a decimal system to reflect main levels of unique tables and listings and sub-levels of replicate tables and listings with two digits per level (e.g., Table XX.YY.ZZ. ...).

- 1. The first level number should be consistent with the corresponding CSR appendix in which the tables or listings will appear. For example, the post text tables usually occupy Appendix 14 and the individual subject data listings are put in Appendix 16. All post text tables should have a main number level 14 and listings 16. The subject accounting and disposition table is usually first in the first section of the report and should be numbered Table 14.1. The supportive subject data listing would be Listing 16.1. A subset by sex table would have the number Table 14.1.2, etc.
- 2. Subject accounting and final disposition should appear as the second level number (Table 14.1 series). Baseline and demographic profile occupies the next sub-level (Table 14.2 series). Efficacy should come next (14.3 series) followed by safety (table 14.4 series). Reasons for subjects' being excluded from efficacy and protocol violation summary tables should appear as the last level (Table 14.5 series). Similar conventions should be applied to the subject data listings.
- 3. The title should be complete, accurate, and concise. The last line of the title should provide the analysis group being summarized (e.g., Intent-to-Treat Subjects or Per-Protocol Efficacy Subjects). If possible,

[name], Ltd Statistical Analysis Plan, Version 2.0

the units of measurement for data contained in the table can appear in parentheses to conserve space in the body of the table. For example, the summary of vital signs title could read "Summary of Sitting and Standing Blood Pressure (mmHg) and Heart Rate (bpm)." Whether in the title or body of a table or listing, units must always be specified for all appropriate data.

4. If possible, variables being summarized and statistics reported should appear in the left most column of a table. The next columns for treatment groups should report the data from left to right for the investigational drug, placebo, comparative agents, and (optional) all treated subjects, respectively.

In general, the listings should be sorted and presented by treatment assignment, investigational site, and subject number. Treatment assignment and site can appear in the banner of the listing. From left to right, the subject number, visit number, visit date, and relative day should appear. All tables and listings must have explanatory notes that give, as a minimum, data extraction date, output generation date, complete program name and path where it is stored, CRF pages from which the data were obtained, and supportive listings or tables supported, as appropriate. The definition of all derived variables and decodes for coded data must appear in the notes. Due to space limitations, tables and listings may require a page of notes as a one-time preface to the output.

6.3. Data Management

Biorasi will create SDTM data sets and ADaM analysis data sets using (SAS®) software. Data analyses and summary tables are generated using SAS version 9.4 or above.

6.4. Data Presentation Conventions

Continuous variables (e.g. age) are summarized using descriptive statistics (the number of subjects with available data, the mean, standard deviation (SD), median and minimum and maximum). Categorical variables (e.g. race) are summarized using counts and percentages. Percentages are calculated using the total subjects per treatment group.

The following conventions are applied to all data presentations and summaries.

For continuous variables, all mean and median values are formatted to one more decimal place than the measured value. Standard deviation values are formatted to two more decimal places than the measured value. Minimum and maximum values are presented with the same number of decimal places as the measured value.

For categorical variables, the number and percentage of responses are presented in the form XX (XX.X %) where the percentage is in the parentheses.

Date variables are formatted as DDMMMYYYY for presentation. Time is formatted in military time as HH:MM for presentation.

Wherever possible, data will be decimal aligned.

P-values, if applicable, will be presented to 4 decimal places. If the p-value is less than 0.0001 then it will be presented as <0.0001.

Unless otherwise stated, any statistical tests performed will use 2-sided tests at the 5% significance level.

The table and listing shells and table of contents as part of this SAP provide the expected layout and titles of the tables, listings and figures. Any changes to format, layout, titles, numbering, or any other minor deviation will not necessitate a revision to the SAP nor will it be considered a deviation from planned analyses. Only true differences in the analysis methods or data handling will necessitate such documentation. The appropriate listings supporting the tables will be included and are not specified in the individual sections throughout the document.

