## **Number of Subjects:**

Approximately 150 subjects with facial acne vulgaris will be randomized at 10 centers to have 120 subjects who complete the study.

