3.2. Study Endpoints

3.2.1. Primary Endpoints

The primary safety endpoints are:

- Local Cutaneous Safety Evaluation Data (dryness, non-lesional erythema, peeling, stinging, burning, and itching). Reactions on the face were assessed separately from those on the chest/back/shoulders.
- Treatment-Emergent Adverse Events (TEAEs).

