6.5.2. Safety Population

All subjects who receive at least one confirmed dose of study product and provide any post baseline safety information will be included in the safety population. No imputation will be made for missing safety data.

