8.3. Analysis of the Efficacy Endpoints

The following efficacy endpoints will be summarized using descriptive statistics for both the ITT and PP populations:

- Proportion of Subjects with IGA Success at Weeks 4, 8 and 12. IGA success is defined as an IGA score of 0 (Clear) or 1 (Almost Clear) with at least a 2-grade reduction from baseline.
- Absolute Change from Baseline in Inflammatory Lesion Counts at Weeks 4, 8 and 12. The following location of lesions will be summarized separately: face and chest/back/shoulders.
- Absolute Change from Baseline in Non-Inflammatory Lesion Counts at Weeks 4, 8 and 12. The following location of lesions will be summarized separately: face and chest/back/shoulders.
- Percent Change from Baseline in Inflammatory Lesion Counts at Weeks 4, 8 and 12. The following location of lesions will be summarized separately: face and chest/back/shoulders.
- Percent Change from Baseline in Non-Inflammatory Lesion Counts at Weeks 4, 8 and 12. The following location of lesions will be summarized separately: face and chest/back/shoulders.
- Change from Baseline to Weeks 4, 8 and 12 in CADI.

For all efficacy endpoints for the ITT and PP populations, data will be summarized at week 4, 8 and 12 with data as is where missing data is not imputed.

Also for missing IGA and lesion counts in the ITT population, data will be summarized at week 12 where the primary handling method for missing data, except for baseline, will be the multiple imputation (MI) approach via regression. In details, the MI regression model will include the following predictors in the model: treatment, age, gender, baseline inflammatory lesion counts, baseline non-inflammatory lesion counts, and the results of the same variable from previous visits. The average score of the MI copies will be used to calculate the summary statistics.

Finally for missing IGA, lesion counts and CADI in the PP population, data will be summarized at week 12 where the primary handling method for missing data will be the Last Observation Carried Forward (LOCF). For the PP population, number of subjects who were discontinued prematurely due to documented lack of efficacy, worsening condition, or a TEAE is expected to be small. For these subjects the efficacy data from their termination visit will be assigned to the nearest corresponding scheduled visit that has been missed, and carried forward to the subsequent visits for the analysis.

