9.2. Local Cutaneous Safety Evaluation

Non-lesional erythema, peeling, dryness, stinging, burning and itching scores will be summarized by treatment group and visit including sample size, frequency count and percentage for each visit. A similar summary will be provided excluding subjects with signs or symptoms present at Baseline.

Non-lesional erythema, peeling, dryness, stinging, burning and itching scores and their corresponding descriptions are listed in Table 7, Table 8, Table 9, Table 10, Table 11 and Table 12 respectively.

Table 7: Scoring of Non-Lesional Erythema

Severity	Score	Description
None	0	No erythema
Mild	1	Light pinkness present
Moderate	2	Definite redness, easily recognized
Severe	3	Intense redness

Table 8: Scoring of Peeling

Severity	Score	Description
None	0	No peeling
Mild	1	Barely perceptible shedding, noticeable only on light scratching or rubbing
Moderate	2	Obvious but not profuse shedding
Severe	3	Heavy scale production

Table 9: Scoring of Dryness

Severity	Score	Description
None	0	No dryness
Mild	1	Slight barely perceptible fine superficial scale
Moderate	2	Clearly perceptible fine scale giving skin a powdery appearance
Severe	3	Marked roughness, cracked skin with fissures

Table 10: Scoring of Stinging

Severity	Score	Description
None	0	No stinging
Mild	1	Slight sharp, tingling/stinging sensation; not really bothersome
Moderate	2	Definite sharp, tingling/stinging sensation; that
		is somewhat bothersome
Severe	3	Sharp, tingling/stinging sensation that has caused definite discomfort

Table 11: Scoring of Burning

Severity	Score	Description
None	0	No burning
Mild	1	Slight warm, burning sensation; not really bothersome
Moderate	2	Definite warm, burning sensation; that is somewhat bothersome
Severe	3	Hot, burning sensation that has caused definite discomfort

Table 12: Scoring of Itching

Severity	Score	Description
None	0	No itching
Mild	1	Slight itching; not really bothersome
Moderate	2	Definite itching that is somewhat bothersome, without loss of sleep
Severe	3	Intense itching that has caused pronounced discomfort; night rest interrupted and excoriation of the skin from scratching may be present

Overall cutaneous tolerance was graded at the Week 12 visit, or the last visit if earlier, using grades shown in Table 13 below.

Table 13: Overall Tolerance

Grade	Score	Description
Excellent	0	No signs of irritation during the study
Good	1	Slight signs of irritation during the study, which resolved by the end of the study

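### By-visit local tolerance percentages default to an all-subjects denominator, so subjects not assessed at a visit dilute every score row of a primary endpoint

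*SAP*

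**What the plan says.** SAP 6.4 (Data Presentation Conventions) says of categorical variables: "Percentages are calculated using the total subjects per treatment group". It is the only general denominator rule in the SAP. The same paragraph has continuous variables report the number of subjects who have data.

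SAP 3.2.1 makes the six local reactions (dryness, non-lesional erythema, peeling, stinging, burning, itching) a primary safety endpoint. SAP 9.2 says the 0 to 3 scores will be "summarized by treatment group and visit including sample size, frequency count and percentage for each visit", and adds: "A similar summary will be provided excluding subjects with signs or symptoms present at Baseline". It names no denominator for either summary. On missing values, SAP 6.5.2 says: "No imputation will be made for missing safety data".

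The tolerability shell (Table 14.2.2.2.1) does not settle the matter. It has Score and Severity columns only, with no count and percentage, no visit N, no missing row and no denominator footnote. By contrast, the physical examination shell (Table 14.3.2) has a Missing row, and the lesion-count shells have a row for subjects evaluated.

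For efficacy, SAP 8.3 says "data will be summarized at week 4, 8 and 12 with data as is where missing data is not imputed". The IGA success shell (Table 14.2.1.1.1) states no percentage base.

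**The concern.** The trial is descriptive. SAP 4.3 says it is not powered for significance, and no model or test stands behind the tolerance tables. The printed percentages therefore are the comparison of DFD-03 with Tazorac. If their denominator includes subjects who were not examined, two things follow.

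- Within an arm, reactions can appear to fade from Week 4 to Week 12 only because fewer subjects are seen.
- Between arms, a difference in follow-up becomes a difference in apparent tolerability.

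Unequal loss tied to the endpoint is foreseeable, because the worst grade of the plan's Overall Tolerance scale is discontinuation for irritation. The same default would affect the non-imputed IGA success rates: with total N underneath, a missing IGA acts as a non-success, although SAP 8.3 says nothing is imputed there.

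**Working it through.** **Inputs from the documents**
- Randomized and completing (Protocol Synopsis): "Approximately 150 subjects with facial acne vulgaris will be randomized at 10 centers to have 120 subjects who complete the study".
- Allocation 2:2:1:1 (SAP 4.4).
- Reaction rates of 10% to 30% for the commonest reactions to tazarotene cream 0.1% (Protocol section 8). These are adverse-reaction rates, used here only as an illustrative range for p.

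**Assumptions**
- Share unassessed at a visit: 20% in both arms, then 10% v 30%, then 15% v 25%. The documents give no loss by arm or by visit.
- A nominal safety population of 50 per active arm. The percentages below do not depend on this number.

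**Plan's own figures.** 150 × 2/6 = 50 and 150 × 1/6 = 25, which matches the 50/50/25/25 in SAP 4.4. The implied overall loss is 1 − 120/150 = 20%. The plan states no visit-level percentage that could be reproduced.

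**Formulas.** Let p be the rate of a reaction (score 1 to 3) among assessed subjects and m the share unassessed. On the all-subjects denominator:
- reaction rows print p × (1 − m);
- the score 0 row prints (1 − p) × (1 − m);
- all rows sum to 1 − m;
- with equal p, the false gap between arms on the reaction rows is p × (m2 − m1).

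**Equal loss, m = 20%.** 10% × 0.8 = 8%; 20% × 0.8 = 16%; 30% × 0.8 = 24%. The rows sum to 80%. There is no gap between arms.

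**Unequal loss, equal true rates (values are expectations)**

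| p | Reaction rows, 10% v 30% loss | Gap | Score 0 row, 10% v 30% loss | Gap in reaction rows, 15% v 25% loss |
|---|---|---|---|---|
| 10% | 9% v 7% | 2 points | 81% v 63% | 1 point |
| 20% | 18% v 14% | 4 points | 72% v 56% | 2 points |
| 30% | 27% v 21% | 6 points | 63% v 49% | 3 points |

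In whole numbers at p = 20%: 9 of 45 assessed and 7 of 35 assessed are both 20.0%. Over 50 they print as 18.0% and 14.0%, and the rows sum to 90% and 70%.

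**How much could be hidden.** At 10% v 30% loss, the arm losing more could have a rate of up to 0.30 × 0.9/0.7 = 38.6% among assessed subjects and still print no worse than an arm at 30%.

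**What the assessed-only base does not cure.** Suppose 15 of 50 subjects react and 10 of those leave (assumed). The all-subjects base shows 5/50 = 10%, the assessed base shows 5/40 = 12.5%, and the proportion who ever reacted is 15/50 = 30%.

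**The case against.** The best defence is that total N is only a default. SAP 9.2 asks for a sample size at each visit, which can be read as the base of the percentage beside it. SAP 6.1 requires tables to show how many subjects the data apply to and to separate not-performed from missing. Either would let a reader see the shortfall. This stands in part: the dilution would be visible to a careful reader. It still leaves two defensible denominators for a primary endpoint, and the only one written down is the one that dilutes.

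Irritated dropouts also leave traces elsewhere: the Overall Tolerance grade, adverse events for worsening from Baseline, TEAEs leading to discontinuation, and Week 12 evaluations at early withdrawal where possible (Protocol 7.7). The safety population already omits anyone with no post-baseline safety information. These points limit the harm but do not correct the by-visit tables.

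Several stronger readings are tempting and are not supported:

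- That the rule governs every percentage. It does not: reasons for discontinuation use the number who discontinued (Table 14.1.1.1).
- That unassessed subjects are scored as reaction-free. They enter no row, and the score 0 row shrinks too.
- That the arm losing more always looks better. This needs unequal loss and true rates close enough not to outweigh it. It holds on the reaction rows only; on the score 0 row that arm looks worse.
- That subjects excluded for baseline signs stay in the denominator of the second summary (9/30 = 30% printed as 9/50 = 18%). SAP 9.2 speaks of excluding them, so this is a strained reading, although no base is stated.
- That chest/back percentages would be printed over the whole arm. The display index lists no separate chest/back tolerance table.

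**Conclusion.** The point holds and should be corrected. Following SAP 6.4 as written, the by-visit tolerance percentages for scores 1 to 3 are understated in proportion to the share unassessed: 8% to 24% in place of 10% to 30% at 20% loss. The 20% is the overall allowance from randomized to completing subjects, so it is an assumption for any one visit, and some who withdraw will have been assessed on leaving.

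Equal loss produces no false difference between arms. A false gap of 2 to 6 points needs something like 10% v 30% loss; at 15% v 25% it is 1 to 3 points. A reader might infer that the plan demonstrably favours DFD-03 or Tazorac. Nothing in the documents supports that, because neither the size nor the direction of any difference in loss is known.

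**What to change.** In SAP 9.2 and the tolerability shell, state the following:

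- By-visit percentages of local tolerance scores use subjects with a non-missing assessment at that visit and location. That n is shown, with a separate row for subjects not assessed.
- The summary without baseline signs uses subjects with score 0 for that reaction at Baseline who are assessed at that visit.
- The non-imputed IGA success rates use subjects with an IGA at that visit. The ITT IGA shell also carries a footnote saying missing values are filled by LOCF, which conflicts with SAP 8.3 and should be reconciled at the same time.

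Add to SAP 6.4 that the total-subjects rule yields where a section names its own base. Keep total N for adverse event incidence and demographics, and the existing bases for disposition.

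Add one complementary table: the worst post-baseline score per subject for each reaction, over the safety population, with any subject lacking a post-baseline score shown in its own row. In the example of 15 reactors it would show 15/50 = 30%, provided their reactions were scored at a visit before or at withdrawal.

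The cost is SAP wording, revised shells and one extra table from data already collected. The displayed reaction percentages will be slightly higher. If the database is already locked, record the change in the study report, as SAP section 2 requires for departures from the approved plan.
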